5.2 Trial Vaccination(s)

The vaccines to be used in this trial are outlined below in Table 1.

Vaccine	Dose/Potency	Dose Frequency	Route of Administration	Vaccination Regimen	Use
VARIVAX [™] PE34 process (Group 1)	0.5 mL after reconstitution	2 doses; 3 months between each dose	Subcutaneous injection	Visit 1 (Day 1) and Visit 3 (Week 13 [Days 91-105])	Investigational
VARIVAX [™] (2016 commercial product) (Group 2)	0.5 mL after reconstitution	2 doses; 3 months between each dose	Subcutaneous injection	Visit 1 (Day 1) and Visit 3 (Week 13 [Days 91-105])	Standard of care
M-M-R [™] II (Groups 1 and 2)	0.5 mL after reconstitution	2 doses; 3 months between each dose	Subcutaneous injection	Visit 1 (Day 1) and Visit 3 (Week 13 [Days 91-105])	Standard of care

Vials of vaccine will be labeled with component identification numbers (CIDs). Care should be taken to ensure that each subject receives the appropriate clinical materials labeled with their specific CID.

Trial vaccinations are given on the day of randomization or as close as possible to the date on which the subject is allocated/assigned. All supplies indicated in Table 1 above will be provided centrally by the Sponsor.

The investigator shall take responsibility for and shall take all steps to maintain appropriate records and ensure appropriate supply, storage, handling, distribution and usage of trial treatments in accordance with the protocol and any applicable laws and regulations.

5.2.1 Dose Selection

5.2.1.1 Dose Selection (Preparation)

The rationale for selection of doses to be used in this trial is provided in Section 4.0 - Background & Rationale. There are no specific calculations or evaluations required to be performed in order to administer the proper dose to each subject.

5.2.2 Timing of Dose Administration

Subjects will be randomized to 1 of 2 vaccination groups to receive either two 0.5-mL subcutaneous doses of VARIVAXTM PE34 process (Group 1) or two 0.5-mL subcutaneous doses of VARIVAXTM (2016 commercial product) (Group 2) approximately 3 months apart. Dose 1 will be administered at Visit 1 on Day 1 of the trial, and Dose 2 will be administered at Visit 3 (Week 13 [Days 91-105]). Each dose of VARIVAXTM PE34 process and VARIVAXTM (2016 commercial product) will be administered concomitantly with M-M-RTM II.

5.2.3 Trial Blinding

A double-blinding technique with in-house blinding will be used. VARIVAXTM PE34 process and VARIVAXTM (2016 commercial product) will be packaged identically so that the blind is maintained. The subject, the investigator and Sponsor personnel or delegate(s) who are involved in the vaccine administration or clinical evaluation of the subjects are unaware of the group assignments.

See Section 7.1.4.2, Blinding/Unblinding, for a description of the method of unblinding a subject during the trial, should such action be warranted.

5.3 Randomization or Vaccine Allocation

Vaccine randomization will occur centrally using an interactive voice response system/integrated web response system (IVRS/IWRS). There are 2 vaccination groups. Subjects will be assigned randomly in a 1:1 ratio to VARIVAXTM PE34 process (Group 1) or VARIVAXTM (2016 commercial product) (Group 2), respectively.

5.4 Stratification

No stratification based on age, sex or other characteristics will be used in this trial.

5.5 Concomitant Medications/Vaccinations (Allowed and Prohibited)

Medications or vaccinations specifically prohibited in the exclusion criteria are not allowed during the ongoing trial. If there is a clinical indication for any medication or vaccination specifically prohibited during the trial, discontinuation from trial therapy or vaccination may be required. The investigator should discuss any questions regarding this with the Sponsor Clinical Director. The final decision on any supportive therapy or vaccination rests with the investigator and/or the subject's primary physician. However, the decision to continue the subject on trial therapy or vaccination schedule requires the mutual agreement of the investigator, the Sponsor and the subject's legally acceptable representative.

All medications administered from 30 days before each trial vaccination through 42 days after each trial vaccination should be recorded on the appropriate eCRF. Subjects should not have received any previous measles-, mumps-, rubella-, or VZV-containing vaccines, either alone or in any combination, or any such vaccines outside of trial protocol for the duration of the trial.

Product: V210 Protocol/Amendment No.: A03-01

Subjects should not have received salicylates (e.g., aspirin or any aspirin-containing products) during the 14 days before Vaccination 1, and should not receive these products until after 42 days after Vaccination 2, because the use of salicylates in children with varicella has been associated with Reye syndrome. Subjects must not have received any immunoglobulin, a blood transfusion, or blood-derived products (does not include autologous blood/blood products) for at least 5 months (150 days) before vaccination and should not receive these products while enrolled in this trial, unless there is a medical necessity warranting their use.

Use of immunosuppressive therapies is reason for exclusion, with the following exceptions:

- 1. Use of topical, ophthalmic, and inhaled steroids is permitted.
- 2. Use of systemic immunomodulatory steroids must meet the following criteria:
 - Subjects should not receive any dose of systemic immunomodulatory steroids within 7 days before or after each vaccination.
 - Subjects should not receive systemic immunomodulatory steroids (no more than the equivalent of 2 mg/kg total daily dose of prednisone or equivalent or >20mg/day of prednisone or equivalent for subjects weighing >10 kg) for more than 7 consecutive days from the time of trial start through the end of the 42-day safety follow-up period Postvaccination 2.

If higher doses of systemic immunomodulatory steroids or other systemic immunosuppressive agents are administered after trial entry but before Vaccination 2, or if the subject otherwise develops an immunosuppressive condition in this interval, then the second dose of trial vaccines should be discontinued.

It is preferable that other vaccines routinely administered to children who are between 12 months to 23 months of age be given outside of the trial period so as not to confound the results from this trial. These vaccines will not be provided by the Sponsor or Sponsor designee. If necessary, enrollment in the trial can be deferred if a medically important vaccine needs to be administered; however, the subject would only be permitted to continue with a delayed vaccination if the visit can be performed within the allowed window. A full 15 days must elapse between the receipt of inactivated nontrial vaccines and enrollment into the trial. A full 31 days must elapse between the receipt of live nontrial vaccines (e.g., yellow fever) and enrollment into the trial.

If medically necessary, both licensed inactivated and live nontrial vaccines may be administered in the interval between Visit 2 and Visit 3. As specified in Section 5.1.3, a minimum of 43 days should elapse between Visit 1 (when the first dose of trial vaccine is administered) and receipt of the inactivated or live nontrial vaccine. In addition:

- If a licensed, inactivated (**nonlive**) vaccine (e.g., IPV, DTaP, Hib) is given between Visits 2 and 3, the second dose of trial vaccine must not be given until at least 15 days have elapsed.
- If a licensed **live** vaccine is given between Visits 2 and 3, the second dose of trial vaccine must not be given until at least 31 days have elapsed.

After the successful completion of trial procedures at Visit 4 (Week 19 [Days 133-147 Postvaccination 1]), both inactivated and live nontrial vaccines may be administered.

5.6 Rescue Medications & Supportive Care

No rescue or supportive medications are specified to be used in this trial.

See Section 7.1.2.1.3, General Precautions for Administration, regarding administration of epinephrine in the event of an anaphylactic reaction.

5.7 Diet/Activity/Other Considerations

No special restrictions on diet or activity apply.

5.8 Subject Withdrawal/Discontinuation Criteria

5.8.1 Discontinuation of Vaccination

Discontinuation of vaccination does not represent withdrawal from the trial.

As certain data on clinical events beyond vaccination discontinuation may be important to the study, they must be collected through the subject's last scheduled follow-up, even if the subject has discontinued vaccination. Therefore, all subjects who discontinue trial vaccination prior to completion of the vaccination period will still continue to participate in the trial as specified in Section 6.0 (Trial Flow Chart) and Section 7.1.5.3 (Discontinued Subjects Continuing to be Monitored in the Trial) unless consent is withdrawn. For subjects who will not receive Vaccination 2, all tasks except vaccination and eVRC should be completed.

Subjects may discontinue vaccination at any time for any reason or be dropped from vaccination at the discretion of the investigator should any untoward effect occur. In addition, a subject may be discontinued from vaccination by the investigator or the Sponsor if vaccination is inappropriate, the trial plan is violated, or for administrative and/or other safety reasons. Specific details regarding procedures to be performed at vaccination discontinuation are provided in Section 7.1.4 – Other Procedures.

A subject must be discontinued from vaccination but continue to be monitored in the trial for any of the following reasons:

- The subject or subject's legally acceptable representative requests to discontinue vaccination.
- The subject has a medical condition or personal circumstance that, in the opinion of the investigator and/or Sponsor, places the subject at unnecessary risk through continued participation in the trial or does not allow the subject to adhere to the requirements of the protocol.
- \circ The subject meets any of the criteria in Section 5.1.3.
- Treatment unblinding.

For subjects who are discontinued from vaccination but continue to be monitored in the trial, all visits and procedures, as outlined in the trial flowchart, except vaccination and eVRC should be completed.

Discontinuation from vaccination is "permanent." Once a subject is discontinued, he/she shall not be allowed to restart vaccination.

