6.0 TRIAL FLOW CHART

Visit Number:	1	2	3	4	5
	Randomization/	Vaccination 1		Vaccination 2	
Visit Title:	Vaccination 1	Follow-up ^a	Vaccination 2 ^b	Follow-up ^{a,c}	Phone Call ^c
Trial Timing:	Week 1	Week 6	Week 13	Week 19	Month 9
Trial Days:	Day 1	Days 43-57	Days 91-105	Days 133-147	Days 271-285
Administrative Procedures					
Obtain informed consent	Х				
Obtain informed consent for future biomedical research ^d	Х				
Assign screening number	Х				
Distribute subject identification card	Х				
Review inclusion/exclusion criteria	Х				
Review deferment/exclusion criteria (before Vaccination 2)			Х		
Review medical history	Х				
Review concomitant medication and nontrial vaccines	Х	Х	Х	Х	
Assign treatment allocation/randomization using IVRS/IWRS	Х		Х		
Laboratory Procedures/Assessments					
Obtain buccal swabs (DNA) for Future Biomedical Research ^d	Х				
Obtain blood sample for immunogenicity testing ^e	Х	Х			
Clinical Procedures/Assessments					
Take temperature (oral or equivalent) ^f	Х		Х		
Administer VARIVAX [™] (left arm [or left anterolateral thigh]) ^f					
Group 1: VARIVAX [™] PE34 process	Х		Х		
Group 2: VARIVAX [™] (2016 commercial product)					
Administer M-M-R [™] II (right arm [or right anterolateral thigh]) ^f	Х		Х		
Observe subject for anaphylaxis or other allergic reaction (at least 30 minutes)	Х		Х		
Distribute eVRC/review instructions with subject/legally acceptable representative ^g	Х		Х		
Review eVRC reports with legally acceptable representative ^h		Х		Х	
Educate subject/legally acceptable representative on serious adverse events definition	Х	х	х	х	
and reporting	Λ		Λ		
Review adverse events and serious adverse events ⁱ		Х	Х	Х	
Collect eVRC device				Х	
Active assessment (using scripted safety questions) for occurrence of possible serious					Х
adverse events and medically attended adverse events					Λ
a. Visit 2 and Visit 4 should be performed no sooner than 42 days after the previous	vaccination.				

b. The subject would only be permitted to continue with a delayed vaccination if the visit can be performed within the 14-day window.
c. For subjects who will not receive Vaccination 2, all tasks except vaccination and electronic Vaccination Report Card should be completed.

Informed consent for optional future biomedical research samples must be obtained to collect the DNA sample. d.

04SDBR

Visit Number:	1	2	3	4	5
	Randomization/	Vaccination 1		Vaccination 2	

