Visit Title:	Vaccination 1	Follow-up ^a	Vaccination 2 ^b	Follow-up ^{a,c}	Phone Call ^c
Trial Timing:	Week 1	Week 6	Week 13	Week 19	Month 9
Trial Days:	Day 1	Days 43-57	Days 91-105	Days 133-147	Days 271-285

e. A 3-mL blood sample will be taken on Day 1, immediately before vaccination with VARIVAXTM and at Week 6 (43-57 days after Day 1 vaccination with VARIVAXTM. The Visit 1 (Day 1) immunogenicity blood sample is mandatory for enrollment. Leftover main trial serum will be stored for future biomedical research if the parent/legally acceptable representative consents to future biomedical research.

f. Before vaccination with trial vaccine, review all eligibility criteria, including subject's temperature. If the subject has a fever (defined as an oral temperature of $\geq 102.2^{\circ}$ F (39.0°C) or equivalent, the subject should not receive trial vaccine and the vaccination visit should be rescheduled until >72 hours after resolution of the febrile illness. If the subject's axillary temperature is \geq 98.6°F (37.0°C), the parent/legally acceptable representative will be requested to further measure and record the subject's rectal temperature in the eVRC. Parents/legally acceptable representatives should only record axillary temperatures and rectal temperatures as indicated. Oral temperatures and otic temperatures should not be recorded by parents/legally acceptable representatives.

g. The eVRC device is dispensed at Visit 1. Only instructions are reviewed at Visit 3.

h. The eVRC (Section 7.1.1.9) is required to be completed for a full 42 days after each vaccination. The eVRC device will be distributed at Visit 1 and returned to the site at Visit 4. At Visit 3, the subject or parent/legally acceptable representative must be reminded to return with the eVRC device at Visit 4.

i. The development of varicella-like, HZ-like, measles-like and rubella-like rashes and mumps-like symptoms through 42 days after vaccination will be recorded on the eVRC. The subject's parent/legally acceptable representative will be instructed to contact trial personnel immediately if a varicella- or HZ-like rash develops. Subjects are required to be seen at the clinic within 72 hours of the rash presentation. Trial personnel will review the completed eVRC reports to identify any unreported occurrences of these specific conditions.

28

04566R

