7.1.2.1.5 Clinical Follow-up

Subjects will be followed for adverse events through 42 days after each vaccination. Specific injection-site reactions will be solicited from Day 1 through Day 5 after vaccination with the trial vaccine (VARIVAXTM PE34 or VARIVAXTM 2016 commercial product) and M-M-RTM II. Daily temperatures will be recorded on an eVRC from Day 1 through Day 42 after vaccination. Regardless of severity or causality, all unsolicited injection-site reactions; and all systemic adverse events, including varicella-, zoster-, measles-, rubella-like rashes and mumps-like symptoms, will be recorded on an eVRC for Day 1 through Day 42 after vaccination. Serious adverse events, including death, will be reported from Day 1 after the first dose of trial vaccine through Day 180 after the second dose of trial vaccine. Medically attended adverse events will be reported from Day 133 through Day 271. During the phone call at Day 271 (Day 180 Postvaccination 2), a scripted questionnaire will be used to determine if any serious adverse events or medically attended adverse events have occurred for each subject since completing the 42-day safety follow-up period Postvaccination 2.

The parent/legally acceptable representative of each subject will record the safety data on the eVRC and return the eVRC to the trial site at Visit 4. Trial personnel will review the eVRC for completeness, accuracy, and clarity. All information will be accurately recorded on the appropriate eCRFs.

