7.1.4.2 Subject Blinding/Unblinding

When the investigator or delegate needs to identify the drug used by a subject and the dosage administered in case of emergency e.g., the occurrence of serious adverse events, he/she will contact the emergency unblinding call center by telephone and make a request for emergency unblinding. As requested by the investigator or delegate the emergency unblinding call center will provide the information to him/her promptly and report unblinding to the Sponsor. Prior to contacting the emergency unblinding call center to request unblinding of a subject's treatment assignment, the investigator or delegate must enter the intensity of the adverse events observed, the relation to study drug, the reason thereof, etc., in the medical chart etc.

Subjects whose treatment assignment has been unblinded by the investigator/delegate and/or non-study treating physician must be discontinued from study drug, but should continue to be monitored in the trial.

Additionally, the investigator must go into the IVRS system and perform the unblind in the IVRS system to update drug disposition. In the event that the emergency unblinding call center is not available for a given site in this trial, IVRS/IWRS should be used for emergency unblinding in the event that this is required for subject safety.

Treatment/Vaccine identification information is to be unmasked ONLY if necessary for the welfare of the subject. Every effort should be made not to unblind the subject unless necessary.

In the event that unblinding has occurred, the circumstances around the unblinding (e.g., date, reason and person performing the unblinding) must be documented promptly, and the Sponsor Clinical Director notified as soon as possible. Only the principal investigator or

delegate and the respective subject's code should be unblinded. Other trial site personnel and Sponsor personnel directly associated with the conduct of the trial should not be unblinded.

At the end of the trial, random code/disclosure envelopes or lists and unblinding logs are to be returned to the Sponsor or designee.

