For this protocol, the following are considered Tier 1 events: elevated temperatures (maximum reported temperature $\geq 102.2^{\circ}$ F [$\geq 39.0^{\circ}$ C] oral equivalent) within Days 1 to 42 after each vaccination; vaccine-specific measles-, rubella-, varicella-, zoster-like rashes, mumps-like symptoms, and injection-site rashes occurring within Days 1 to 42 after each vaccination; and solicited injection-site reactions (redness, swelling, pain/tenderness) within Days 1 to 5 after each vaccination. In addition, the broad clinical categories consisting of the percentage of subjects with any adverse experience, a vaccine-related adverse experience, a serious adverse experience, an adverse experience that is both vaccine-related and serious, and who discontinued due to an adverse experience will be considered Tier 2 endpoints. The *p* values (Tier 1 only) and 95% CIs (Tier 1 and Tier 2) will be provided for between-group differences in the percentage of subjects with events; these analyses will be performed using the Miettinen and Nurminen method, an unconditional, asymptotic method [17].

Extended Safety Follow-up Period (Day 133 [+14 days] to Day 271 [+14 days])

For the extended safety follow-up period, a summary will be provided of the number of subjects in each vaccination group who report a serious adverse experience or a medically attended adverse experience. For this extended safety follow-up period, these events will be treated as Tier 2 events, with 95% CIs being presented for the between-group risk differences in the percentage of subjects reporting these events. For serious adverse experiences, a

summary along with a between-group comparison will also be provided for the entire trial (i.e., from enrollment through 180 days Postvaccination 2).

Because many 95% CIs may be provided without adjustment for multiplicity, the CIs should be regarded as a helpful descriptive measure to be used in review, not a formal method for assessing the statistical significance of the between-group differences in adverse experiences.

Safety Tier	Safety Endpoint [†]	p Value	95% CI for Treatment Comparison	Descriptive Statistics
	Rate of elevated temperatures (≥ 102.2°F [39.0°C]) [‡] from Days 1 to 42 postvaccination	Х	X	Х
Tier 1	Vaccine-specific systemic rashes (measles-like, rubella-like, varicella- like, zoster-like), mumps-like symptoms, and injection-site rashes Days 1 to 42 postvaccination	Х	X	Х

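### Section 5.8.1 waives the eVRC for children discontinued from vaccination without limiting the waiver to the dose 2 diary, which conflicts with flow-chart footnotes c and h

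*Combined protocol and SAP*

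**What the plan says.** Section 5.8.1 states the waiver twice. One sentence reads: "For subjects who will not receive Vaccination 2, all tasks except vaccination and eVRC should be completed". The closing one, on children discontinued from vaccination but still monitored, says that "all visits and procedures, as outlined in the trial flowchart, except vaccination and eVRC should be completed". Neither separates the diary for dose 1 from the diary for dose 2. The same section gives its purpose: for data on clinical events after discontinuation, "they must be collected through the subject's last scheduled follow-up, even if the subject has discontinued vaccination".

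The flow chart (Section 6.0) repeats the waiver as footnote c: "For subjects who will not receive Vaccination 2, all tasks except vaccination and electronic Vaccination Report Card should be completed". Its marker stands on Visits 4 and 5 only. Visit 2, the dose 1 follow-up where the eVRC is reviewed, does not carry it. Footnote h says that the eVRC "is required to be completed for a full 42 days after each vaccination", with no exception for discontinued children.

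On data sources, Section 7.1.2.1.5 says: "Daily temperatures will be recorded on an eVRC from Day 1 through Day 42 after vaccination". Section 7.1.1.9 has the investigator or delegate review the eVRC at Visits 2 and 4 and enter its data into the eCRF. Section 8.6.2 places fever through Day 42 in Tier 1, along with rash-type events through Day 42 and "solicited injection-site reactions (redness, swelling, pain/tenderness) within Days 1 to 5 after each vaccination".

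**The concern.** There are two doses, so a discontinuation of vaccination always comes after dose 1, and Section 5.8.1 allows it at any time. It is mandatory on a representative's request, on meeting a Section 5.1.3 criterion (a seizure is among them), and on unblinding. Section 7.1.4.2 repeats that unblinded subjects "must be discontinued from study drug, but should continue to be monitored in the trial". Any of these can occur before Day 42, while the dose 1 diary is still running.

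A site that applies Section 5.8.1 literally on that day would end the diary. Daily temperatures that were never taken cannot be recovered. The loss would also be selective, because an adverse reaction can prompt the discontinuation, the unblinding or the parent's request. If such losses were concentrated in one group, that group's fever rate could be understated.

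**Working it through.** **1. The rules side by side, for a child discontinued before Day 42 after dose 1**

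| Place | What it implies for the dose 1 diary |
|---|---|
| Section 5.8.1, closing sentence | Waived; no dose named |
| Section 5.8.1, sentence on children not receiving Vaccination 2 | Waived; which diary is meant is left open |
| Footnote c | Waiver marked at Visits 4 and 5, so it points to the dose 2 diary |
| Footnote h | Required for 42 days after each vaccination |
| Section 5.8.1, stated purpose | Data collection continues after discontinuation |

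The cross-references do not settle it. Section 5.8.1 cites Section 7.1.5.3 as covering discontinued subjects who remain monitored, but the actual Section 7.1.5.3 describes only the Visit 4 follow-up and the Visit 5 phone call. Section 7.1.4, also cited, does not mention the eVRC.

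**2. What is lost on the literal reading**

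- *Fever, Days 1 to 42.* The eVRC is the only scheduled source of daily temperatures. The flow chart has site temperatures at Visits 1 and 3 only. Section 8.6.2 uses the maximum reported temperature, so an unmeasured day cannot supply an event. Illustration for one child stopped after Day 10: 42 − 10 = 32 days unrecorded, and 32/42 = 76%.
- *Solicited injection-site reactions, Days 1 to 5.* Affected only if the stop falls inside that window. Stopped after Day 2: 5 − 2 = 3 of 5 days. Stopped after Day 5: none.
- *Rashes, mumps-like symptoms and injection-site rashes, Days 1 to 42.* The diary prompt goes, and with it the eVRC check for unreported cases described in footnote i. The events remain reportable: Section 7.2 requires all adverse events through 42 days after a live vaccine, and the flow chart lists adverse-event review at Visit 2 in a row separate from eVRC review.

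On the reading in footnotes c and h, no dose 1 diary data are lost.

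**3. Precision**

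No figure in the plan is in dispute. Table 5 (300 per group, about 80% power, 2-sided α = 0.05) is the nearest one that assumes complete dose 1 safety data. With the pooled-variance normal approximation,

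power = Φ{ [d − 1.96·√(2p̄(1−p̄)/n)] / √([p₁(1−p₁) + p₂(1−p₂)]/n) }.

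For 10% against 17.9%, d = 0.079 and p̄ = 0.1395. At n = 300 this is (0.079 − 0.0554)/0.0281 = 0.838, so power is 79.9%. All seven Table 5 rows give 79.4% to 80.2%, so the table reproduces.

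The documents give no rate of discontinuation within 42 days of dose 1. *Assumption:* between 0.5% and 5% of each group drops out of the eVRC-based dose 1 endpoints.

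| Assumed loss | n per group | Power, 10% vs 17.9% |
|---|---|---|
| 0 | 300 | 79.9% |
| 0.5% | 298 | 79.6% |
| 1% | 297 | 79.5% |
| 2% | 294 | 79.1% |
| 5% | 285 | 77.8% |

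At a 10% control rate the detectable difference moves from 7.9 to at most 8.1 points. Loss of precision is minor. What remains is the selectivity of the loss.

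**The case against.** The strongest reply is that the plan, read as a whole, already means the dose 2 diary. The closing sentence of Section 5.8.1 defers to the flow chart, and there the waiver sits on Visits 4 and 5 while footnote h keeps the diary going for 42 days after each dose. This stands to the extent that a reader who infers that the protocol orders sites to stop the dose 1 diary goes further than the text. It does not remove the conflict: the section that sites consult when a child is discontinued has no such limit, and its cross-reference leads to a section that does not address the matter.

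Second, some triggers usually surface late. The formal review of Vaccination 2 exclusions, including seizure and allergic reaction, is scheduled at Visit 3 (Days 91 to 105), after the dose 1 diary has ended. This stands as a reason to expect few cases. Early unblinding, an early parental request or an investigator's early decision remain possible.

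Third, the endpoints are percentages of subjects with an event. A child stopped because of a fever or rash has normally had that event recorded already, and later diary days cannot undo it. This also stands. What can be missed is a first qualifying fever in a child stopped for some other reason.

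**Conclusion.** The conflict is real and should be resolved. On the literal reading the firm loss is the remaining daily temperatures after dose 1, plus solicited items if the stop falls within Days 1 to 5. The number of children affected cannot be derived from the documents and is probably small.

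Three stronger inferences are tempting and are not supported:

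- *That all remaining Tier 1 data are lost.* Rash-type events stay reportable through Day 42, and nothing solicited remains after Day 5.
- *That unrecorded days count as event-free.* Section 8.5.2 keeps these children in the ASaT population, but neither it nor Section 8.6.2 says how incomplete diaries are handled. The direction of any bias therefore depends on an unstated rule and on how the losses fall between groups.
- *That the effect can be sized from the 5% in Section 8.9.2.* That figure is for children who fail to return for the second vaccination phase, not for children discontinued but monitored within 42 days. The same section expects every child to be evaluable after dose 1. Counting affected children is also not counting missed first events, so a comparison with the detectable differences in Table 5 would mislead.

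The case for acting is that the stated rule, if followed, selectively loses safety data that cannot be recovered, and that it is cheap to correct. Which children should be discontinued, and when, is not in question here.

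**What to change.** In both Section 5.8.1 sentences, limit the waiver to Vaccination 2 and to the eVRC for the period after Vaccination 2. Add that the eVRC is completed through Day 42 after the last vaccination received and that the dose 1 eVRC is reviewed at Visit 2. Leave footnote c on Visits 4 and 5 and footnote h as it is; Section 5.8.1 then agrees with both. Correct the cross-reference to Section 7.1.5.3, either by pointing it to text on discontinued children or by removing it.

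The cost is a short wording change in a protocol amendment and a note to sites. No visit or device is added: the family holds the eVRC device from Visit 1 until Visit 4, and Visit 2 takes place in any case. Sample size and analyses are unchanged.
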